**VOLUMETRIC VISUAL FIELDS AT INTERMEDIATE AND NEAR
DISTANCES IN PRESBYOPIC PATIENTS USING OCCUPATIONAL
AND GENERAL-PURPOSE PROGRESSIVE ADDITION LENSES**

Single-center, randomized, double-blind, crossover clinical trial evaluating differences in volumetric visual fields at intermediate and near distances among three progressive addition lens (PAL) designs in presbyopic patients.

Acronym: CIVIUS2025PAL

SICEIA-2025-001629

Investigators:

[name]

[name]

September 20th 2025

Study Protocol Summary

Title:

Single-center, randomized, double-blind, crossover clinical trial evaluating differences in volumetric visual fields at intermediate and near distances among three progressive addition lens (PAL) designs in presbyopic patients.

Brief Summary

Presbyopia is an age-related condition characterized by progressive loss of accommodation, resulting in reduced near and intermediate visual performance, visual fatigue, and decreased comfort during daily tasks. Progressive addition lenses (PALs) are commonly prescribed to compensate for presbyopia. General-purpose PALs (GP-PALs) are designed to provide vision correction from distance to near vision, whereas occupational PALs (PC-PALs) are optimized for intermediate and near visual tasks, particularly for office and computer use.

Although previous studies have evaluated visual satisfaction and performance with different PAL designs, no studies to date have quantitatively assessed the volumetric extent of clear vision between 4 m and 25 cm using different PAL configurations.

The aim of this clinical trial is to compare the volumetric clear vision fields produced by three PAL designs:

- one general-purpose PAL (VIMAX FIT FRM),
- and two occupational PALs (VIMAX PC 1.5 FWD 4 m and VIMAX ZOOM 1.5 FWD 4 m),

all with plano distance power and +2.00 D near addition.

This is a single-center, cross-sectional, randomized, double-blind, crossover clinical trial conducted at the Faculty of Pharmacy, University of Seville. Approximately 23 to 66 presbyopic participants aged 52–67 years will be enrolled according to inclusion and exclusion criteria.

Each participant will undergo:

- ocular and refractive anamnesis,
- visual acuity assessment,
- accommodative amplitude measurement,
- objective refraction,
- binocular vision screening,
- ocular motility and visual field screening tests.

Participants will sequentially test the three PAL designs in randomized masked order. Using validated optotypes positioned at 4 m, 2 m, 1.33 m, 80 cm, 40 cm, and 25 cm,

horizontal and vertical limits of clear vision will be measured while head movements are restricted.

The primary outcome measure is the volumetric clear vision field (cm^3) generated between 4 m and the corneal apex for each lens design, calculated using a quadrangular frustum geometric model. Secondary outcomes include visual field surface areas at each testing distance and analysis of accommodative amplitude according to age, sex, and near-work habits.

The study is designed to evaluate differences in functional visual performance among PAL designs and to support personalized prescription strategies for presbyopic patients, particularly those requiring optimized intermediate and near vision for occupational tasks.

Study Design

- Interventional clinical trial
- Randomized
- Double-blind
- Crossover assignment
- Single-center
- Cross-sectional

Primary Outcome Measure

Volumetric clear vision field (cm^3) between 4 m and 25 cm for each PAL design.

Secondary Outcome Measures

- Visual field surface area at each tested distance

Population

Presbyopic adults aged 52–67 years with reduced accommodative amplitude (<3 D) and adequate binocular visual function.

Data Protection

Participant data will be pseudonymized and stored securely in password-protected electronic files and locked physical storage accessible only to the investigators. Data will be retained for one year and subsequently destroyed according to institutional data protection regulations.

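### The primary volume names a frustum model but fixes neither formula nor segmentation; a sum of prismatoid slabs over the six measured planes would settle both at no cost in data

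*Protocol*

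**What the plan says.** The Brief Summary describes optotypes "positioned at 4 m, 2 m, 1.33 m, 80 cm, 40 cm, and 25 cm", at which "horizontal and vertical limits of clear vision will be measured while head movements are restricted". Width and height are therefore both available at six planes, which bound five segments. The primary outcome is a volume "generated between 4 m and the corneal apex for each lens design", and it is "calculated using a quadrangular frustum geometric model".

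The heading Primary Outcome Measure defines the same quantity as "Volumetric clear vision field (cm^3) between 4 m and 25 cm for each PAL design". The surface area at each distance is a secondary outcome.

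The protocol gives no volume formula. It does not say whether the model is one solid or a stack of segments. It gives no field width, height or width-to-height ratio for any lens.

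**The concern.** The protocol names the geometric model that turns twelve measured dimensions (six widths, six heights) into the primary endpoint, but leaves open two choices that change the result.

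- **Shape.** The frustum of a pyramid has similar ends, and its usual volume formula uses only the two end areas. The separately measured widths and heights then enter only through their product. If the width-to-height ratio differs between planes, the formula no longer gives the volume of the solid through the measured limits.
- **Segmentation.** The model is named in the singular, for the whole region from 4 m inward, with no mention of a sum. A single solid between the end planes would ignore the fields at 2 m, 1.33 m, 80 cm and 40 cm. The trial compares a general-purpose lens with lenses described as optimised for intermediate and near tasks, so these planes matter most to its question.

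The endpoint could thus depend on a choice that the text does not make.

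**Working it through.** The protocol states no volume or error figure, so there is none to reproduce.

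**Inputs.** Planes at 400, 200, 133, 80, 40 and 25 cm come from the Brief Summary. All field shapes below are assumptions. Cross-sections are taken as rectangles w × h, and L is the distance between two planes. Rhombi drawn on the same limits give the same percentages.

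**Formulas for one slab.**

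- Frustum: V_F = L/3 (A1 + A2 + √(A1·A2)), with A = w·h.
- Straight-edged solid (prismatoid): V_P = L/6 (2w1h1 + 2w2h2 + w1h2 + w2h1).
- Difference: V_P − V_F = L/3 [ (w1h2 + w2h1)/2 − √(w1h1w2h2) ].

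By the arithmetic-geometric mean inequality the difference is never negative. It is zero only if w1/h1 = w2/h2.

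**Check.** Take 3 × 1 to 1 × 2 with L = 1, a 6-fold change of ratio.

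- V_P = (6 + 4 + 6 + 1)/6 = 2.833, and numerical integration also gives 2.833.
- V_F = (3 + 2 + √6)/3 = 2.483, which is 12.4% lower.
- With similar ends (4 × 2 to 2 × 1) both formulas give 4.667.

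**Shortfall in one slab with equal end areas**

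| Change in width-to-height ratio | Shortfall |
|---|---|
| 1.25-fold | 0.21% |
| 1.5-fold | 0.68% |
| 2-fold | 1.98% |
| 4-fold | 7.69% |

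It is smaller when the end areas differ. A 2-fold change gives 1.70% at an area ratio of 4 and 1.14% at 16.

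**Shortfall in the total over five stacked slabs** (three assumed area profiles: constant angle, constant area, narrowed far field)

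| Where the shape changes | 2-fold | 4-fold | 8-fold |
|---|---|---|---|
| Gradually, 4 m to 25 cm | 0.07–0.08% | 0.28–0.32% | 0.62–0.72% |
| All between 4 m and 2 m | 1.1–1.5% | 4.3–5.9% | not run |
| Back and forth at every slab | 1.7–2.0% | not run | not run |

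The 4 m to 2 m slab weighs most. Under a constant angular field it holds (400³ − 200³)/(400³ − 25³) = 87.5% of the volume.

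**One solid against stacked slabs.** Each dimension is set to distance × an assumed factor at the six planes. The single solid uses V_F between 400 and 25 cm, and the stack uses V_P.

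| Factors, 4 m to 25 cm | Width and height scaled | Width only scaled |
|---|---|---|
| 1, 0.6, 0.6, 0.6, 0.8, 0.8 | ratio 1.33 (+33%) | 1.17 (+17%) |
| 1, 1.3, 1.3, 1.2, 1, 1 | ratio 0.81 (−19%) | 0.90 (−10%) |

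Now take two lenses with identical fields at 4 m and 25 cm, and width factors of 0.6 against 1.2–1.3 in between. The stacked volume of the second is about 30% larger. The single-solid volumes are equal by construction.

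**Inner bound.** Closing the last 25 cm as a pyramid to the cornea adds about 0.02% of the total under a constant angular field, and about 2.2% under constant area.

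**The case against.** The strongest case on the other side has four parts.

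- **The criticised formula is not in the protocol.** A loosely named quadrangular frustum could be computed by a prismatoid rule, which has no such shortfall, and computational detail is often left to the SAP. This stands as a reason not to call the calculation wrong. It does not remove the point, because the protocol itself chose to name the model that defines its primary endpoint, and read literally that model assumes similar ends.
- **A reader might infer a bias that differs between the lenses.** The document does not support this. It gives no dimensions for any lens and does not say that field shape varies with distance or by design. The shortfall could be zero, or equal across lenses in this within-person comparison.
- **A reader might infer that the protocol plans a single frustum.** The wording names a type of model, not a number of solids. Six planes with an area at each fit a stack at least as well. The 10–33% shifts therefore describe one possible reading under invented profiles.
- **The prismatoid is also an interpolation.** The field between planes is not measured, so the shortfall is relative to straight edges and not to the true field. This stands. The prismatoid does, however, use the widths and heights themselves and needs no assumption of constant shape.

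**Conclusion.** The point holds as a gap in the definition of the primary endpoint, with a conditional error attached to it.

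- **Shape.** If the area-only frustum formula is used and the width-to-height ratio changes between planes, the volume is understated relative to the straight-edged solid and never overstated. With stacked slabs this is small: mostly about 0.1–2%, and about 4–6% only if a 4-fold change falls between 4 m and 2 m. Larger totals would need more extreme opposing changes of width and height.
- **Segmentation.** This is the larger exposure. Only under a single-solid reading would the mid-range planes drop out and the volume shift by the 10–33% illustrated.

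All these sizes rest on assumed field shapes. No difference in error between the lenses can be computed from the document. The two inner bounds are a contradiction in the text itself and need reconciling whatever the formula.

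**What to change.** Define the primary volume as the sum of slabs between adjacent measured planes, each V = L/6 (2w1h1 + 2w2h2 + w1h2 + w2h1), where L is the distance between the planes and w and h are the measured width and height. This equals the frustum formula when the shapes are similar and uses all six planes. The frustum value can be reported as a sensitivity figure if wanted.

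State one inner bound in both places. If it is 25 cm, there are five slabs. If it is the corneal apex, add a segment from 25 cm to the cornea and say how it is computed.

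The cost is a sentence or two in the protocol and one formula in the calculation sheet. No new measurement is needed. Fixing it before the data are analysed also removes a choice between formulas that could give different lens comparisons.
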